
- Change in APRI score and Fib-4 score from baseline to Week 72 and all visits (every 16 weeks) during the optional extension period.
- Change in PELD/MELD score from baseline to Week 72 and all visits (every 16 weeks) during the optional extension period.
- Change in use of UDCA and/or Rifampicin at Weeks 24, 48, and 72.
- Proportion of responders for pruritus scores using the Albireo ObsRO instruments by visit (proportion of patients achieving meaningful reduction based on the clinically meaningful threshold of 1.0 point, which is estimated from the distribution-based and anchor-based approaches in the blinded psychometric analysis)

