4.4 Safety Evaluation

Safety criteria are as follows:

- The primary safety analysis for this study will include the incidence of total treatment-emergent adverse events (TEAEs) and TEAEs categorised by causality, severity, and seriousness assessments made by the Investigator.
- Trends in safety will also be evaluated for the following:
 - Physical examinations
 - Concomitant medications
 - Vital signs
 - Laboratory test results (including clinical chemistry, haematology, urinalysis, alfa-fetoprotein [AFP], vitamins A and E, 25-hydroxy vitamin D, and INR)
 - Abdominal ultrasound
 - Discontinuations due to AEs

5. Sample Size and Power

There is no formal hypothesis testing in this open-label study. The sample size for Cohort 1 was determined in Study A4250-005. For Cohort 1, patients will be enrolled after completion of Study A4250-005 or participation of 12 weeks in that study. For the other endpoints, mainly descriptive analyses will be performed.

The proportion of patients with at least 1 event (i.e., surgical bile diversion, liver transplantation, death) that can be expected in a non-treated population depends on PFIC type and age distribution of the included patients. The expected proportion of patients with events will be calculated for the study population once each patient's age and PFIC type are known, using the probability that a patient will get an event estimated from the reference population in the ongoing observational cohort study, NAtural Course and Prognosis of PFIC and Effect of Biliary Diversion (NAPPED).

As an example, if the expected proportion of patients with at least 1 event is estimated to be 30% in the study population, and then if the proportion of patients with at least 1 event during odevixibat long-term treatment is shown to be only 10% in the study, the power is approximately 89% to 96% (1-sided test, alpha=2.5%) for a confidence interval (CI) with upper boundary <30% based on a sample size of n=48 to 60. The sample size of 60 for Cohort 2 was estimated based on the availability of target patient population to evaluate the therapeutic benefit for those patients.

6. Interim Analysis

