8.1 Handling of Missing Data and/or Invalid Data and Outliers

8.1.1 Missing Data Analysis Methods for Efficacy Endpoints

No imputation will be made for any missing data. The assessments after intercurrent events (death, or initiation of rescue treatments such as biliary diversion surgery or liver transplantation) or follow-up assessments (\geq last dose day + 15 days) will be excluded from analysis with the exception of the analysis of patients undergoing biliary diversion surgery or liver transplantation. For eDiary data analysis, data after last dose will be excluded from analysis.

9. Statistical Methods

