⁸ <https://www.cdc.gov/nccdphp/dnpao/growthcharts/resources/sas-who.htm> following WHO's method

⁹ Abdel-Rahman, Susan M et al. "Construction of Lambda, Mu, Sigma Values for Determining Mid-Upper Arm Circumference z Scores in U.S. Children Aged 2 Months Through 18 Years." *Nutrition in clinical practice* : official publication of the American Society for Parenteral and Enteral Nutrition vol. 32,1 (2017): 68-76.

The number and percent of patients achieving positive pruritus assessment for more than 50% of the time will be summarised by treatment group. Both AM and PM pruritus assessments will be included in the analysis of this endpoint. A cumulative distribution function (CDF) plot showing proportions of patients achieving positive pruritus assessment for more than X% of the time, X is the time of achieving positive pruritus assessment from 0 to 100%, by treatment group will be provided.

❖ Proportion of Responders for Pruritus Scores

The proportion of responders for pruritus scores will be tabulated by visit based on monthly scores and bi-weekly scores. The 95% CI of the proportion of responders will be provided, based on the exact method of Clopper-Pearson. A responder is defined as a patient who reports a decrease in pruritus score from unrounded baseline equivalent to or greater than the threshold of meaningful change estimated from the blinded psychometric analysis; the results of the blinded psychometric analysis across all anchors support a threshold of 1.0 point for AM, PM and AM and PM scratching scores. Baseline 1 and 2, defined in the table of derived variables in [Appendix A](#), will be used for data analysis. Baseline 1 will only be used for patients in Cohort 1 who were on odevixibat in Study A4250-005.

❖ Biliary Diversion Surgery and Liver Transplantation

Number and percent of patients undergoing biliary diversion surgery and/or liver transplantation will be summarised by using descriptive statistics. A 95% CI also will be presented for the corresponding percentage. These parameters will be evaluated separately and together at Weeks 24, 48, 72 and all visits (every 16 weeks) during the optional extension period.

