Weeks 44 – 46	288 – 322	Weeks 42 – 46 (21 days)
Weeks 47 – 48	323 – 378	Weeks 47 – 54 (14 days)
Weeks 58 – 60	379 – 455	Weeks 55 – 65 (21 days)
Weeks 68 – 70	456 – 490	Weeks 66 – 70 (21 days)
Weeks 71 – 72	491 – 504	Weeks 71 – 72 (14 days)
Weeks 72 – 76	>=505	>=505 (28 days)

^a The proportion of positive pruritus assessments is calculated based on reported data only. The assessments after intercurrent events (premature treatment discontinuation, death, or initiation of rescue treatments such as biliary diversion surgery or liver transplantation) will be excluded from the calculation.

^b To have an appropriate analysis, only include patients who reported at least 50% of expected data during the interval. Of notes, for Weeks 34 – 36, while eDiary data during weeks 25 to 41 will be included for analysis, 50% rule is applied to Weeks 31 – 41 only to make sure that a patient is on treatment long enough for the analysis of Weeks 34 – 36.

Table 8: Analysis Visit Window for Proportion of Responders for Pruritus Monthly Scores

4-WEEK/BY-VISIT INTERVAL	INTERVALS TO INCLUDE EDIARY DATA (DAYS) ^a	INTERVALS WITH >=50% OF EXPECTED DATA TO INCLUDE PATIENTS ^b (# OF EXPECTED DAYS TO REPORT EDIARY)
Weeks 1 – 4	1 – 28	Weeks 1 – 4 (28 days)
Weeks 5 – 8	29 – 56	Weeks 5 – 8 (28 days)
Weeks 9 – 12	57 – 84	Weeks 9 – 12 (28 days)
Weeks 13 – 16	85 – 112	Weeks 13 – 16 (28 days)
Weeks 17 – 20	113 – 140	Weeks 17 – 20 (28 days)
Weeks 21 – 24	141 – 168	Weeks 21 – 24 (28 days)
Weeks 34 – 36	169 – 287	Weeks 31 – 41 (21 days)
Weeks 45 – 48	288 – 378	Weeks 42 – 54 (28 days)
Weeks 58 – 60	379 – 455	Weeks 55 – 65 (21 days)
Weeks 68 – 72	456 – 504	Weeks 66 – 72 (28 days)

^a The proportion of responders for pruritus monthly scores is calculated based on reported data only. The assessments after intercurrent events (premature treatment discontinuation, death, or initiation of rescue treatments such as biliary diversion surgery or liver transplantation) will be excluded from the calculation.

^b To have an appropriate analysis, only include patients who reported at least 50% of expected data during the interval. Of notes, for Weeks 34 – 36, while eDiary data during weeks 25 to 41 will be included for analysis, 50% rule is applied to Weeks 31 – 41 only to make sure that a patient is on treatment long enough for the analysis of Weeks 34 – 36.

Table 9: Analysis Visit Window for Proportion of Responders for Pruritus Bi-weekly Scores

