BI-WEEKLY/BY-VISIT INTERVAL	INTERVALS TO INCLUDE EDIARY DATA (DAYS) ^a	INTERVALS WITH >=50% OF EXPECTED DATA TO INCLUDE PATIENTS ^b (# OF EXPECTED DAYS TO REPORT EDIARY)
Weeks 1 – 2	1 – 14	Weeks 1 – 2 (14 days)
Weeks 3 – 4	15 – 28	Weeks 3 – 4 (14 days)
Weeks 5 – 6	29 – 42	Weeks 5 – 6 (14 days)
Weeks 7 – 8	43 – 56	Weeks 7 – 8 (14 days)
Weeks 9 – 10	57 – 70	Weeks 9 – 10 (14 days)
Weeks 11 – 12	71 – 84	Weeks 11 – 12 (14 days)
Weeks 13 – 14	85 – 98	Weeks 13 – 14 (14 days)
Weeks 15 – 16	99 – 112	Weeks 15 – 16 (14 days)
Weeks 17 – 18	113 – 126	Weeks 17 – 18 (14 days)
Weeks 19 – 20	127 – 140	Weeks 19 – 20 (14 days)
Weeks 21 – 22	141 – 154	Weeks 21 – 22 (14 days)
Weeks 23 – 24	155 – 168	Weeks 23 – 24 (14 days)
Weeks 35 – 36	239 – 252	Weeks 35 – 36 (14 days)
Weeks 47 – 48	323 – 336	Weeks 47 – 48 (14 days)
Weeks 59 – 60	407 – 420	Weeks 59 – 60 (14 days)
Weeks 71 – 72	491 – 504	Weeks 71 – 72 (14 days)

^a The proportion of responders for pruritus bi-weekly scores is calculated based on reported data only. The assessments after intercurrent events (premature treatment discontinuation, death, or initiation of rescue treatments such as biliary diversion surgery or liver transplantation) will be excluded from the calculation.

^b To have an appropriate analysis, only include patients who reported at least 50% of expected data during the interval. Of notes, for Weeks 35 – 36, while eDiary data during weeks 35 to 36 will be included for analysis, 50% rule is applied to Weeks 35 – 46 only to make sure that a patient is on treatment long enough for the analysis of Weeks 35 – 36.

Table 10: Analysis Visit Window for Proportion of Positive Pruritus Assessment

CUMULATIVE INTERVAL	INTERVALS TO INCLUDE EDIARY DATA (DAYS) ^a (# OF EXPECTED DAYS TO REPORT EDIARY)	INTERVALS WITH >=50% OF EXPECTED DATA TO INCLUDE PATIENTS ^b (# OF EXPECTED DAYS TO REPORT EDIARY)
Weeks 0 – 4	1 – 28 (28 days)	Weeks 1 – 4 (28 days)
Weeks 0 – 12	1 – 84 (84 days)	Weeks 9 – 12 (28 days)
Weeks 0 – 22	1 – 154 (154 days)	Weeks 19 – 22 (28 days)
Weeks 0 – 24	1 – 168 (168 days)	Weeks 21 – 24 (28 days)
Weeks 0 – 36	1 – 287 (189 days)	Weeks 31 – 41 (21 days)
Weeks 0 – 46	1 – 322 (210 days)	Weeks 42 – 46 (21 days)
Weeks 0 – 48	1 – 378 (224 days)	Weeks 47 – 54 (14 days)
Weeks 0 – 60	1 – 455 (245 days)	Weeks 55 – 65 (21 days)
Weeks 0 – 70	1 – 490 (266 days)	Weeks 66 – 70 (21 days)
Weeks 0 – 72	1 – 504 (280 days)	Weeks 71 – 72 (14 days)

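### The by-visit pruritus responder rate covers only patients still on drug, unoperated and reporting, so late rates may exceed a rate that counts treatment failures and can rise through attrition alone

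*SAP*

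**What the plan says.** Section 4.2 lists, among the secondary endpoints, the "proportion of patients achieving meaningful reduction based on the clinically meaningful threshold of 1.0 point", by visit, on the observer-reported scratching score. Section 9.6.4 makes it binary: "A responder is defined as a patient who reports a decrease in pruritus score from unrounded baseline equivalent to or greater than the threshold", which is set at 1.0 point. It asks for monthly and bi-weekly versions with a Clopper-Pearson 95% CI. The same section bases secondary analyses on the FAS unless otherwise specified, and Section 7 defines the FAS as every patient dosed in this study.

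The handling of patients who leave is in Appendix B.

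- **Footnote a, Table 8 (monthly):** "The proportion of responders for pruritus monthly scores is calculated based on reported data only".
- **Footnote a, Table 9 (bi-weekly):** "The proportion of responders for pruritus bi-weekly scores is calculated based on reported data only".
- **Both footnotes a:** assessments after premature discontinuation, death, biliary diversion or liver transplantation are excluded.
- **Both footnotes b:** only patients with at least 50% of expected diary data in the interval are included. The stated reason is that the patient should have been on treatment long enough.

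Section 8.1.1 adds that "No imputation will be made for any missing data" and removes diary data after the last dose. The SAP contains no non-responder rule, composite definition or sensitivity analysis for this endpoint.

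**The concern.** Together these rules make the by-visit rate conditional. It is the share of responders among patients who are still on drug, have not been operated on and are still completing the diary. The SAP itself classes diversion and transplantation as rescue treatments. Loss of patients for lack of benefit is also foreseeable: Section 3.1 admitted to Cohort 1 patients who had left the parent study because they saw no improvement or had intolerable symptoms. Leaving may therefore be related to the outcome.

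The Cohort 1 objective in Section 2.1 is a sustained effect. A by-visit responder curve will be read as evidence on that objective. If patients who do badly drop out of the denominator, the curve can hold or climb while the number of responders stays the same or falls. Nothing in the planned responder analysis would show this.

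**Working it through.** **The SAP's only design figure.** Section 5 gives 89% to 96% power for an upper confidence bound below 30% when the true event proportion is 10%, with n = 48 to 60. With an exact binomial calculation and a Clopper-Pearson upper bound, success needs at most 7/48 or at most 10/60 events. The power is then 0.898 and 0.966, so the figure reproduces. It concerns diversion, transplantation and death, not the responder endpoint. It is used here only as the source of a 10% illustration: "if the proportion of patients with at least 1 event during odevixibat long-term treatment is shown to be only 10% in the study".

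**Inputs.** N = 60 is the planned Cohort 2 size (Section 5). The number excluded by a late visit, m, is not given; 10% matches the Section 5 example, and 20% and 30% are assumptions. The responder share among those observed is assumed to be about 60%.

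**Formulas.** With x responders, the SAP rate is x/(N − m). If all m are counted as non-responders, the rate is x/N. The ratio of the two is N/(N − m), never below 1 and growing as m accumulates. At 10% excluded it is 60/54 = 1.11.

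| Excluded | SAP rule (95% CI) | All m as non-responders (95% CI) | Gap, points |
|---|---|---|---|
| 6 (10%) | 32/54 = 59.3% (45.0–72.4) | 32/60 = 53.3% (40.0–66.3) | 5.9 |
| 12 (20%) | 29/48 = 60.4% (45.3–74.2) | 29/60 = 48.3% (35.2–61.6) | 12.1 |
| 18 (30%) | 25/42 = 59.5% (43.3–74.4) | 25/60 = 41.7% (29.1–55.1) | 17.9 |

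Over observed rates of 50% to 70%, the gap is 5–7 points at 10% excluded, 10–14 at 20% and 15–21 at 30%.

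**Only some leavers are failures.** If 6 of 12 excluded patients count as failures and 6 are missing for other reasons, the failure-counting rate is 29/(48 + 6) = 53.7%, between the two columns.

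**Attrition alone.** Hold 30 responders of 60 constant and let only non-responders leave. The SAP rate goes from 30/60 = 50.0% to 30/54 = 55.6%, 30/48 = 62.5% and 30/42 = 71.4% as 6, 12 and 18 leave. The rate with leavers kept in stays at 50.0%. This is the extreme case.

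**The other direction.** Suppose the target were the response had everyone stayed on drug, with 60% observed and every leaver a would-be responder. The true rate would be (0.6 × 54 + 6)/60 = 64%, (0.6 × 48 + 12)/60 = 68% or (0.6 × 42 + 18)/60 = 72%. The SAP rate would then be too low.

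**The case against.** The SAP names its intercurrent events and applies the exclusion consistently to its diary responder and positive-assessment endpoints. That can be read as a deliberate while-on-treatment summary, which is legitimate in a single-arm, descriptive extension without formal testing. It also keeps relief brought by surgery from being credited to the drug. Surgery has its own endpoint with a CI, Kaplan-Meier curves cover surgery and death (Section 9.6.4), and disposition gives reasons for discontinuation (Section 9.2). At 10% excluded, the 5.9-point shift is under half the CI half-width of (72.4 − 45.0)/2 = 13.7 points.

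Much of this stands, and it rules out three stronger readings.

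- A reader might infer that every such event is a drug failure with a known pruritus value. The responder definition concerns scratching only, and a patient may have met it up to the event. Counting the patient as a non-responder is a convention.
- A reader might infer that the output carries an FAS label that its denominator contradicts. Table templates are in a separate document (Section 1), and footnote b openly restricts the patients included.
- A reader might take the 10% as expected attrition. It is a hypothetical in a power example.

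Separate reporting does not settle the matter, however. It neither corrects the responder rate nor shows, visit by visit, who was removed and why. The UDCA/rifampicin shift table in the same section has a category for early termination; the responder analysis gives leavers no place.

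**Conclusion.** The point holds in a limited form. The by-visit responder rate is conditional on remaining on drug, unoperated and reporting. Late-visit rates may therefore be overstated relative to a definition that counts treatment failures, and they can rise through attrition alone. That they are overstated outright cannot be said, because against a had-they-stayed target the bias could run the other way.

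The size cannot be determined from the SAP. At N = 60 and about 60% observed response, the gap is about 6 points if 10% are excluded, and 12 and 18 points at the assumed 20% and 30%. These figures treat every excluded patient as a failure and are smaller otherwise. A patient whose event comes late in an interval, with half the entries already made, still counts in that interval. The endpoint is secondary and descriptive, so what is affected is the reported rate and its CI, not an error rate. This is an inexpensive improvement to interpretation, and it leaves the planned analysis in place.

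**What to change.** In Section 9.6.4 and footnotes a and b of Tables 8 and 9, add a second responder analysis for the monthly and bi-weekly scores:

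1. Among patients with a non-missing baseline score, those who have had biliary diversion, liver transplantation, death, or discontinuation for lack of effect or adverse event stay in the denominator as non-responders in every interval after the event.
2. Patients whose interval score is missing for any other reason are left out of both numerator and denominator for that interval.
3. State how the interval containing the event is scored when the 50% rule is not met.
4. Show this rate, with its Clopper-Pearson CI, beside the reported-data-only rate, and give the number excluded at each visit by reason.

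The data are already planned for: discontinuation reasons and surgery status are in disposition (Section 9.2), and early leavers are telephoned up to Week 72 about diversion and transplantation (Section 3.1). The cost is one extra derivation, revised wording and somewhat lower reported late responder rates.

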4.1 Primary Efficacy Endpoints

The primary efficacy endpoints are as follows:

- **EU and Rest of the World (RoW):** Change from baseline in fasting serum bile acids after 72 weeks of treatment.

Change from baseline will be calculated based on the average of the values at Weeks 70 and 72. The baseline fasting serum bile acids value is defined as follows unless otherwise specified:

Cohort 1: The average of the last 2 values before the first dose of study drug in Study A4250-008. In general, these 2 values are the values of the last 2 assessments of Study A4250-005. If pre-dose assessments are collected in Study A4250-008 for a patient, then the values of pre-dose assessments in Study A4250-008 will be considered first and used to calculate the baseline. These 2 values need to be taken from 2 consecutive scheduled visits or unscheduled visits. If only one value is available from 2 consecutive scheduled visits or unscheduled visits, then that value will be used as baseline.

Cohort 2: The average of the last 2 values before the first dose of study drug in Study A4250-008.

- **United States (US):** Proportion of positive pruritus assessments at the patient level over the 72-week treatment period using the Albireo ObsRO instrument. A positive pruritus assessment is defined as a scratching score of ≤ 1 or at least a one-point decrease from baseline on the Albireo ObsRO instrument. At each assessment, the AM score will be compared to the baseline AM average, and the PM score will be compared to the baseline PM average. Both AM and PM pruritus assessments will be included in the analysis of this endpoint. AM scores from the period of 14 days before or on the first dose day in Study A4250-008 will be averaged as the AM baseline. PM scores from the period of 14 days before the first dose day in Study A4250-008 will be averaged as the PM baseline. If a patient's baseline average score is ≤ 1 , then only the criterion of a one-point drop from baseline on the Albireo ObsRO instrument will be used to determine whether a pruritus assessment is positive or not for the primary endpoint analysis.

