This study is an extension study of Study A4250-005 and was ongoing at the time of the New Drug Application (NDA) and Marketing Authorisation Application (MAA) submission in November 2020. For the NDA/MAA submission purposes, the database was locked on 31Aug2020 for Study A4250-005, and an interim analysis of Study A4250-008 with data cut on 15Jul 2020 was performed to accompany the final analyses of Study A4250-005.

For this interim analysis submitted in the NDA/MAA, the analyses described in this SAP were conducted, as appropriate, based on data available at the time of the data cut-off date. The interim analysis was conducted for both safety and efficacy mainly based on descriptive statistics. The main time point was at the end of 24-week treatment period

while all data were included for by-visit summaries. These analyses accompanied the Study A4250-005 analyses and provided further information regarding the safety and efficacy of odevixibat dosing for more than 24 weeks.

For supporting a post-marketing commitment, an interim analysis of Study A4250-008 (planned data cut of 31July2022) was performed in order to update the CSR. The selected analyses described in this SAP were conducted, as appropriate, for the interim analysis based on data available at the time of the data cut-off date. The interim analysis was conducted for both safety and efficacy mainly based on descriptive statistics.

Analyses may be performed at select time points throughout the collection of patient data for regulatory requirements and sponsor decision making purposes.

7. Analysis Sets

The FAS will consist of all patients who received at least 1 dose of study drug in Study A4250-008. The FAS will be the primary analysis set for all analyses unless otherwise specified.

8. Statistical Considerations and Analysis

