
VARIABLES	FORMULA
Average of change from baseline from each AM and PM scores (scratching, itch severity)	
The calculation below is based on the change from baseline in each AM and PM score. The values based on this calculation will be used for data analysis.
 
Change from baseline (daily) will be calculated by averaging all non-missing values of change from baseline (AM and PM) in a day. A daily change from baseline will be considered missing if both AM and PM change from baseline in a day are missing.
 
Change from baseline (weekly) will be calculated by averaging all non-missing values of change from baseline (AM and PM) in a week. A weekly change from baseline will be considered missing if ≥ 8 out of 14 change from baseline values in a week are missing.
 
Change from baseline (monthly) will be calculated by averaging all non-missing values of change from baseline (AM and PM) in a month (28 days). A monthly change from baseline will be considered missing if ≥ 29 out of 56 assessments in a month are missing.
 
Change from baseline at each visit after Week 24 will be calculated by averaging all non-missing values of change from baseline (AM and PM) between 2 visits with analysis windows applied (Appendix B). 50% rule is applied based on the number of planned assessments.

Baseline, daily, weekly, and monthly (sleep parameters, such as difficulty falling asleep and staying asleep, tiredness, the number of awakenings)	For patient- and observer-reported outcome scores of sleep parameters, the same approach above will be used as for scratching/itch severity by AM and PM, respectively, since there is just one rating per day.
Proportion of positive pruritus assessments	No imputation will be made for any missing data. The assessments after intercurrent events (premature treatment discontinuation, death, or initiation of rescue treatments such as biliary diversion surgery or liver transplantation) will be treated as missing and excluded from analysis. The proportion of positive pruritus assessments will be calculated based on reported eDiary data only. 50% rule will be applied based on the number of planned assessments (Appendix B).

VARIABLES	FORMULA

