^a The proportion of positive pruritus assessments is calculated based on reported data only when >=50% of expected ediary data is reported. The assessments after intercurrent events (premature treatment discontinuation, death, or initiation of rescue treatments such as biliary diversion surgery or liver transplantation) will be excluded from the calculation.

^b To have an appropriate analysis, only include patients who reported at least 50% of expected data during the interval. Of notes, for Weeks 0 – 36, while eDiary data during weeks 0 to 41 will be included for analysis, 50% rule is applied to Weeks 31 – 41 only to make sure than a patient is on treatment long enough for the analysis of Weeks 0 – 36.

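### The Weeks 0–72 pruritus proportion admits only patients who report at least half of the last fortnight's diary, so a result labelled FAS is close to a completer result

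*SAP*

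**What the plan says.** SAP Section 4.1 defines the US primary endpoint as "Proportion of positive pruritus assessments at the patient level over the 72-week treatment period using the Albireo ObsRO instrument". Section 4.2 makes the same proportion a secondary endpoint for the EU and RoW.

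Section 7 sets the population: "The FAS will consist of all patients who received at least 1 dose of study drug in Study A4250-008". It adds: "The FAS will be the primary analysis set for all analyses unless otherwise specified". Section 9.6.3 repeats the FAS basis for the primary analyses, with the same qualifier.

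Appendix A, Table 3 says of this endpoint that a "50% rule will be applied based on the number of planned assessments" and refers to Appendix B. There, the Weeks 0–72 row of Table 10 has two separate intervals. Data come from Days 1–504, with 280 expected diary days. Inclusion of the patient is decided on Weeks 71–72 only, with 14 expected days. Footnote b states the inclusion rule: "only include patients who reported at least 50% of expected data during the interval". It explains the purpose for one row, as being "to make sure than a patient is on treatment long enough for the analysis of Weeks 0 – 36".

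Section 8.1.1 rules out imputation and drops diary data after the last dose. Appendix A and Table 10 footnote a also drop assessments after premature treatment discontinuation, death or rescue surgery.

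**The concern.** The inclusion rule selects patients on something that happens after baseline: still being on treatment, and still filling in the diary, in the last two weeks of a 72-week period. A patient who stops at Week 60 has about 60 weeks of experience relevant to the endpoint, and none of it enters the estimate. What is reported as the FAS result is then a result in patients who stayed to the end and reported at the end.

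This matters because Cohort 1's primary objective in Section 2.1 is a sustained effect. Patients who stop for lack of benefit are part of the evidence on that question. The excluded set also carries over to the 95% confidence interval for the proportion and to the subgroup analyses of the primary endpoints. No listed sensitivity analysis for the 72-week proportion puts these patients back.

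**Working it through.** **1. Reproduce the plan's denominator.** The diary is daily for 24 weeks (168 days) and then covers the 21 days before each clinic visit. Only 14 days are available where visits are two weeks apart. The expected days are 168 + 21 + 21 + 14 + 21 + 21 + 14 = 280. The running totals 168, 189, 210, 224, 245, 266 and 280 match Table 10 from Week 24 on.

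**2. Who can pass the Weeks 71–72 condition?** The window is Days 491–504, that is 14 days or 28 AM and PM entries.

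- Last dose on Day 496: at most 496 − 490 = 6 days. 6/14 = 12/28 = 42.9%, so the patient is removed whether days or entries are counted.
- Last dose on Day 497: at most 7 days. 7/14 = 14/28 = 50%, so the patient is kept if the diary is complete.

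Every patient with a last dose on or before Day 496 is therefore out. A patient on treatment throughout who reports only 6 of the 14 days is out as well.

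**3. How much diary is discarded?** For a fully compliant patient, the share of the 280 expected days already reported at the stop is:

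| Treatment stops after | Days reported | Share of 280 | In Weeks 0–72 row? |
|---|---|---|---|
| Day 140 | 140 | 50% | No |
| Day 168 | 168 | 60% | No |
| Day 252 | 189 | 67.5% | No |
| Day 378 | 224 | 80% | No |
| Day 490 | 266 | 95% | No |

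All five would meet a 50% rule applied to the whole interval.

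**4. Effect on the reported mean.** Let d be the fraction of patients removed, R the mean proportion in retained patients and X the mean in removed patients. Table 10 reports R. The mean over everyone is (1 − d)R + dX. The difference is d(R − X).

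The SAP gives none of d, R or X. The values below are assumptions that show a range.

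| d | R 0.60, X 0.40 | R 0.60, X 0.20 | R 0.70, X 0.20 |
|---|---|---|---|
| 5% | +0.01 | +0.02 | +0.025 |
| 10% | +0.02 | +0.04 | +0.05 |
| 20% | +0.04 | +0.08 | +0.10 |
| 30% | +0.06 | +0.12 | +0.15 |

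For example, with d = 20%, R = 0.60 and X = 0.40, the mean over everyone is 0.8 × 0.60 + 0.2 × 0.40 = 0.56, against 0.60 reported. If R = X the shift is zero.

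**The case against.** The best defence is that the rule is deliberate and disclosed. Section 7 makes the FAS primary only where nothing else is specified, and Table 10 does specify something else. A reader might infer that the SAP flatly contradicts its own analysis set; that qualifier means it does not. What stands is that the estimate is still presented as an FAS result without saying that it is restricted in this way.

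Section 5 states that there is no formal hypothesis testing, and Section 9.6.3 summarises this endpoint descriptively with a confidence interval. No success criterion depends on it. That lowers the severity.

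A reader might also infer that discontinued patients vanish from the report. They do not. They appear in each earlier cumulative row whose own window they meet. The patient with a full diary to Week 70 is in the Weeks 0–70 row with 266 days. Discontinuations with reasons (Section 9.2) and surgery and transplantation (Section 9.6.4) are reported separately. This makes attrition visible, but it does not repair the 72-week estimate.

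Footnote a of Table 10 has its own 50% condition, which can be read as applying to the whole interval. On that reading a completeness check already exists alongside the last-fortnight condition. It adds a filter and does not lift the other one.

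Four stronger readings are not supported:

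- **Established upward bias.** The SAP gives no discontinuation rate and no outcome by discontinuation status, so size and direction are both conditional.
- **One missed entry removes an extension participant whose Visit 11 falls on Day 497.** Such a patient stops the diary with 7 of 14 days available. The statement holds only if AM and PM entries are counted, as Appendix A suggests. Table 10 counts days, and a day with one of its two entries may still count.
- **The same fault in Tables 8 and 9.** Table 8 footnote a says "The proportion of responders for pruritus monthly scores is calculated based on reported data only", and Table 9 is alike. These are observed rates for single intervals and discard no earlier data. Counting discontinued patients as non-responders there is a preference about the estimand.
- **Early weighting as an error.** Weeks 1–24 supply 168/280 = 60% of diary days because of the diary schedule, not Table 10. By-interval summaries already show the later course.

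**Conclusion.** The point holds for the Weeks 0–72 row of Table 10. Read with the exclusion of diary data after the last dose and the absence of imputation, the inclusion rule removes everyone whose last dose is on or before about Day 496, together with treated patients who report too little of the last fortnight. The retained set is close to completers and slightly narrower, since some completers fail on diary gaps; patients who stop in the final week can still qualify.

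That patients are removed follows from the text. The numerical consequence does not. A shift of +1 to +15 points rests on assumed removal of 5–30% and assumed mean differences of 0.2–0.5 in favour of retained patients. This should be fixed because it bears on a primary endpoint, but it is not critical because the analysis is descriptive.

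**What to change.** For the cumulative rows of Table 10, and at least for Weeks 0–72:

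1. Remove the last-interval condition. Include every FAS patient with a valid baseline and at least 50% of planned assessments reported up to the earlier of treatment stop and the end of the interval.
2. Reword footnotes a and b together, so that a whole-interval reading of footnote a does not still exclude compliant patients who stop before Day 140. State whether the 50% counts days or AM and PM entries.
3. Keep the gated version as a supportive analysis, and label it as restricted to patients with diary data in Weeks 71–72.
4. Report the number excluded under each rule, with reasons.

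A version that counts planned assessments after discontinuation as not positive may be added as a sensitivity analysis. Replacing the main estimand, changing Tables 8 and 9, or weighting by calendar time is optional and not part of this fix.

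The cost is SAP wording and a small amount of reprogramming, and the resulting proportion may be less favourable. Patients who stop early will also contribute proportions based on few assessments. Section 6 describes interim analyses with 2020 and 2022 data cuts, so the change should be recorded as made after those analyses and both versions shown.
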